1 PROTOCOL SUMMARY

1.1 SYNOPSIS

Title	NIcotinamide Riboside in SARS-CoV-2 pAtients for reNAl protection (NIRVANA)			
Study Description	A pilot, double-blind, placebo-controlled, multicenter, interventional clinical trial with oral nicotinamide riboside (NR) 500 mg (versus placebo) twice daily for a total of 10 days in hospitalized participants with COVID-19.			
Objectives	Primary			
	 To determine the effect of nicotinamide riboside (NR) on whole blood NAD+ levels in hospitalized patients with COVID-19 infection and AKI during the 10-day intervention period; To evaluate the safety of NR in patients with COVID-19 infection and AKI during the 10-day intervention period; 			
	Secondary			
	 To determine the effect of NR on changes in area under curve (AUC) serum creatinine from baseline during the 10-day intervention; To determine the effects of NR on serum creatinine AUC, dialysis, and death with an ordinal categorical outcome having four categories (labeled 1, 2, 3, 4), defined as, in order from least to most severe disease, 1. Serum creatinine AUC < median, 2. Serum creatinine AUC ≥ median, 3. Dialysis, 4. Death during the 90d period post randomization; To determine the effect of NR on MAKE (Major Adverse Kidney Events; composite criteria defined as development or progression of chronic kidney disease, the initiation of long-term dialysis, or death from any cause) at 30d and 90d post randomization; To determine the effect of NR on degree of kidney impairment defined with estimated glomerular filtration rate (eGFR) and proteinuria at 30d and 90d post randomization; 			
	Exploratory			
	• To determine the relationship of whole blood NAD+ levels with AUC creatinine and surrogate markers of AKI such as kidney injury molecule- 1 (KIM-1) and neutrophil gelatinase-associated lipocalin (NGAL);			
Endpoints	Primary			
	 Rates of change in whole blood NAD+ level from baseline to day 10 in NR compared to Placebo. Safety of NR in hospitalized patients with COVID-19 and AKI (defined as the occurrence of at least one serious adverse event of grade 3 or higher or the occurrence of thrombocytopenia (>25% decline in blood platelet count from baseline value). 			

	Secondary				
	 Rates of change in AUC serum creatinine benchmarked to baseline from baseline to day 10 in NR compared to Placebo; An ordinal categorical outcome with four categories (labeled 1, 2, 3, 				

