3 OBJECTIVES AND ENDPOINTS

OBJECTIVES	ENDPOINTS	JUSTIFICATION FOR		
		ENDPOINTS		
Primary				
 To determine the effect of nicotinamide riboside (NR) on whole blood NAD+ levels in hospitalized patients with COVID-19 infection and AKI during the 10-day intervention period; To evaluate the safety of NR in patients with COVID-19 infection and AKI during the 10-day intervention period. 	 The primary endpoint is the rate of change in whole blood NAD+ level over the 10 day period from baseline to day 10. Safety of NR in hospitalized patients with COVID-19 and AKI (defined as the occurrence of at least one serious adverse event of grade 3 or higher or the occurrence of thrombocytopenia defined as >25% decline in blood platelet count from baseline. 	 Recent clinical data indicate a reduction of blood NAD+ level in AKI patients and an increase in NAD+ in 48 hrs with NR treatment; The safety of NR in COVID-19 patients is not known 		
Secondary	-	-		
• To determine the effect of	• The rate of change in AUC	• The recovery of AKI, as		
NR on changes in AUC	benchmarked to baseline;	assessed by AUC serum		

Table 2: Study objectives, endpoints, and justification for endpoints

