Potential participants who may have severe AKI or advanced CKD will be considered with a binary independent variable in the models addressing this condition with corresponding displays of the line and whisker plots by treatment group and summary tables of coefficients, standard errors and p-values. Interactions between this binary variable and treatment will be of interest and will be described.

Capture and tabulation of concomitant medications, dialysis, co-enrollment in another COVID-19 clinical trial, any new standard of care, pre-existing CKD, and treatments by study arm (NR, Placebo) may be used to define other potential adjustments with binary or categorical variables to be defined post hoc in exploratory analyses. Such models may motivate extended interpretations of any treatment effects found.

PRIMARY END POINT: Safety

All reportable AEs will be listed by Preferred Term by subject, treatment, clinical site, grade, relation to treatment, severity, and seriousness. All unanticipated events will be listed by treatment and clinical site with a detailed description of each event, incident, experience or outcome. An unblinded statistician will summarize safety data periodically for the DSMB.

AEs will be tabulated by treatment and clinical site, displaying, for each event, the number and percentage of participants experiencing at least one Grade 3 or 4 occurrence and he null hypothesis to be tested is H_0 : $p_{NR}=p_{Placebo}$ where p_{NR} and $p_{Placebo}$ are the probabilities of experiencing at least one Grade 3 or Grade 3 event in the NR and Placebo groups. H_0 will be tested with Fisher's Exact test, overall and by clinical site. Additionally, treatment groups will be contrasted on the occurrence at least once of each event with Fisher's exact test. All statistical testing will be two-sided with a significance level of 5%.

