9.4.4 SAFETY ANALYSES

Please see section 9.4.2 ANALYSIS OF THE PRIMARY EFFICACY ENDPOINT

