9.4.6 PLANNED INTERIM ANALYSES

An O'Brien-Fleming procedure will be used to conduct an interim analysis for safety when 50% of the patients complete the study. A statistical basis for stopping the study at the first look will be achieved if the test statistic for the primary safety endpoint (the occurrence of at least one serious adverse event of grade 3 or higher or the occurrence of thrombocytopenia less than 50,000 per microliter) indicates harm in the NR arm at p \leq 0.003. If the test statistic does not reach p \leq 0.003 at the first look then the trial will proceed to the final analysis. The statisticians (Drs. [name] and [name]) will inform the principal investigator if the interim analysis crosses the boundary in the direction of harm is observed (p \leq 0.003). A treatment effect will be declared harmful at the final analysis if the test statistic indicates harm and p \leq 0.047. The safety data will be summarized at interim analysis. The statisticians will inform the DSMB if there are any safety concerns at the interim analysis. Any decision on stopping the study based on safety will be made in coordination with NIDDK and the DSMB.

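### The primary safety endpoint has three incompatible definitions, and the composite stated in the synopsis and Section 3 is not the endpoint of any planned test

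*Combined protocol and SAP*

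**What the plan says.** - **Synopsis (1.1) and Section 3, Table 2.** The endpoint is the "occurrence of at least one serious adverse event of grade 3 or higher or the occurrence of thrombocytopenia". The platelet part is spelled out in Table 2 as "the occurrence of thrombocytopenia defined as >25% decline in blood platelet count from baseline". The matching objective is "To evaluate the safety of NR in patients with COVID-19 infection and AKI during the 10-day intervention period".
- **Section 9.4.2, primary safety endpoint.** Adverse events (AEs) are tabulated with "the number and percentage of participants experiencing at least one Grade 3 or 4 occurrence". The null hypothesis tested overall and by site is equality of the "probabilities of experiencing at least one Grade 3 or Grade 3 event in the NR and Placebo groups", by two-sided Fisher's exact test at 5%. In addition, "treatment groups will be contrasted on the occurrence at least once of each event", also by Fisher's exact test.
- **Section 9.4.4, Safety Analyses.** The whole text is "Please see section 9.4.2 ANALYSIS OF THE PRIMARY EFFICACY ENDPOINT".
- **Section 9.4.6, interim analysis.** The endpoint is again called the primary safety endpoint, but its second component is "the occurrence of thrombocytopenia less than 50,000 per microliter". Harm is judged at p ≤ 0.003 at the interim look and p ≤ 0.047 at the final analysis.
- **Section 2.1.** Each of the three scenarios leading to a later trial requires that NR show no significant excess of harm. No test is named for that condition.

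**The concern.** Safety is one of two primary endpoints. If 9.4.2 and 9.4.6 are followed as written, they answer different safety questions, and neither is the one stated in the synopsis. Whoever applies the Section 2.1 scenarios could choose between the two tests after seeing the data. Section 5.5 also pauses enrolment after 50 participants for the DSMB to review primary outcome data, so the ambiguity arises during the trial as well.

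The platelet part is not incidental. Section 2.3.1 reports a statistically significant mean platelet fall of 20,000/µL in a dose-escalation study of NR, and transient thrombocytopenia with nicotinamide in haemodialysis patients. The overall test in 9.4.2 drops platelets, and 9.4.6 narrows them sharply.

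**Working it through.** The plan gives no power figure for safety, so there is none to reproduce.

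**1. Definitions side by side**

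| Element | 1.1 and Section 3 | 9.4.2 overall test | 9.4.6 |
|---|---|---|---|
| Event must be serious | yes | no | yes |
| Grades | 3 or higher | 3 or 4 (misprinted) | 3 or higher |
| Grade 5 (death, 8.3.3.1) | in | out | in |
| Platelets | decline above 25% | none | below 50,000/microL |
| Final level | not stated | 0.05 | 0.047 |

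A death with no earlier Grade 3/4 event, or a platelet fall above 25% that is not graded 3/4, counts in the first column and not in the second. A non-serious Grade 3/4 event counts only in the second; Section 8.3.3.1 itself separates severe from serious.

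**2. The two platelet criteria.** Section 5.2 excludes counts below 100,000/microL.
- The 25% criterion is met below 0.75 × baseline: 75,000 from a baseline of 100,000, and 150,000 from 200,000.
- The 50,000 criterion needs a fall above (baseline − 50,000)/baseline: 50% from 100,000, and 75% from 200,000.

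Any count below 50,000 is a decline above 25% whenever baseline is at least 50,000/0.75 = 66,667. The 9.4.6 criterion is therefore a strict subset of the stated one.

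**3. Effect on the conclusion (assumed rates).** Inputs from the plan: 100 randomized (5.5), 1:1 (6.1.1), so 50 per arm. Assumptions:
- Grade 3/4 SAEs occur at the same rate q in both arms, with no other Grade 3/4 events.
- Further falls above 25%, neither Grade 3/4 nor below 50,000, occur independently at rate f: 10% on placebo and a higher rate on NR.

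Composite rate = q + (1 − q) × f. For q = 0.10 and f = 0.30 versus 0.10: 0.10 + 0.90 × 0.30 = 0.37, and 0.10 + 0.90 × 0.10 = 0.19. The probability of two-sided Fisher p ≤ 0.05 with more events on NR, by exact binomial enumeration:

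| Falls, NR vs placebo | Stated composite, q = 10% / 20% / 40% | Per-event test on falls alone |
|---|---|---|
| 20% vs 10% | 13% / 10% / 7% | 19% |
| 30% vs 10% | 44% / 31% / 18% | 64% |
| 40% vs 10% | 78% / 63% / 38% | 93% |

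The overall endpoints of 9.4.2 and 9.4.6 both reduce to q versus q here: 0.9% / 1.4% / 1.6%.

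**4. A constructed result.** Ten participants per arm have a Grade 3/4 SAE; a further 12 on NR and 1 on placebo have a platelet fall as in step 3.
- Stated composite: 10 + 12 = 22 versus 10 + 1 = 11, p = 0.033.
- Overall tests of 9.4.2 and 9.4.6: 10 versus 10, p = 1.00.
- Per-event test on falls, if no other participant has one: 12 versus 1, p = 0.0018.

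If those 12 and 1 are instead non-serious Grade 3/4 events without a platelet fall, only the overall test of 9.4.2 shows p = 0.033.

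**5. Final level.** At 50 per arm, four harm-direction tables have p between 0.047 and 0.05: 15 vs 6 and 44 vs 35 (p = 0.0479), and 20 vs 10 and 40 vs 30 (p = 0.0486). With assumed placebo rates of 10% to 70% and an NR excess of 0, 10 or 20 points, the chance of landing on one is 0 to 1.9%.

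**The case against.** **The plan would still see a platelet signal.** This is the strongest reply, and much of it stands. Section 8.3.4 flags a fall above 25% as an AE without a grade condition, and 9.4.2 compares the arms event by event. In the illustration that test has more power than the stated composite. A reader might infer from the p = 1.00 above that the plan is blind to platelet harm; the documents do not support that. But the test works only if falls are entered as AEs. Section 8.3.6 exempts thrombocytopenia from AE reporting unless it is judged related or of uncertain relationship, and lists a fall above 25% under its SAE-reporting exemption heading. A per-event comparison is also not the primary endpoint.

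**No composite is tested at the end.** A reader might infer this too, and it is wrong. Section 9.4.6 carries a composite to a final rule, with the narrower platelet criterion.

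**The time window is undefined.** This goes too far. The objective names the 10-day intervention period, and Table 2 sets it beside the endpoint. Recording events to Day 90 (8.3.4) is a collection period and does not by itself set a competing window.

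**The illustration is built to show a gap.** True: SAE rates are set equal, and 30% versus 10% has no source in the documents. Section 2.3.1 lists platelet reductions under 10% as a rare risk of unknown rate, and cites a placebo-controlled nicotinamide trial that found no thrombocytopenia. The figures show what can happen, not what is likely.

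**It is an exploratory pilot with independent safety review.** Also true, and participant protection does not rest on this p-value alone. That does not excuse a primary endpoint without a single definition.

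The misprinted grade is only a typing error, and the point does not depend on it. The platelet limit in Section 7.2 is a rule for stopping study drug, not a fourth endpoint definition.

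**Conclusion.** The contradiction holds on the text alone. The three definitions differ in seriousness, in whether death counts and in the platelet criterion. The stated composite is never tested, two overall tests compete at the final analysis, and Section 2.1 is tied to neither.

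The choice of definition can reverse the safety conclusion: 44% to 18% against 0.9% to 1.6% in the central illustration. Those figures rest on assumed rates, independent components and 50 analysed per arm, and they describe the overall tests only. The per-event test partly covers the platelet component, conditional on AE entry. Deaths enter the ordinal and MAKE analyses of Section 9.4.3, but not as a test of harm. The gap between 0.05 and 0.047 needs tidying but has almost no numerical effect.

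**What to change.** 1. Use one composite in 9.4.2 and 9.4.6: at least one SAE of grade 3 or higher, Grade 5 included, or one platelet criterion. The sponsor must reconcile the 25% decline with the 50,000 count; this review does not choose between them.
2. Test it overall with Fisher's exact test over the 10-day intervention period named in the objective, at one final level. Sections 9.4.2 and 9.4.6 must agree on that level.
3. State that events exempt from AE reporting under 8.3.6, such as unrelated death and thrombocytopenia, still count toward the composite. Take platelet falls from laboratory values, not from AE reports.
4. Name this test in Section 2.1 as the one that decides whether harm is significantly increased.
5. Keep the Grade 3/4 and per-event comparisons as supporting tables.

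The cost is mainly wording, because SAEs, deaths and platelet counts are already collected. The real weakness is platelet data after early discharge. Section 8.2 ties the safety laboratory to hospitalized participants, Table 4 lists platelets again at Days 30 and 90, and Section 8.1 describes the Day 10 home draw as research laboratory and biorepository work. The plan should say whether a platelet count is run on that draw, and report by arm how many participants have no count after discharge.

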A dose escalation study was performed in 8 healthy subjects in a non-randomized, open-label pharmacokinetics (PK) study with 250 mg NR orally administered on days 1 and 2, then uptitrated to peak dose of 1000 mg twice daily on days 7 and 8. No clinically significant changes were seen at NR dose up to 1000 mg orally twice daily in any of the five pre-specified safety endpoints, i.e., potassium, creatine phosphokinase (CPK), glucose, uric acid and alanine aminotransferase. Serum potassium decreased by an average of 0.4 mEq/L, which was statistically significant (p = 0.015) but the individual levels remain in normal range. There was a slight though statistically significant decrease for hematocrit (mean difference = -2%, p = 0.005), hemoglobin (-0.4 g/dL, p = 0.04), and platelet count (-20,000/µL, p = 0.03). There were no significant changes in blood pressure, body temperature, body weight, white blood cell count, lactate dehydrogenase or aspartate aminotransferase. In addition, there were no significant changes in serum levels of sodium, chloride, urea nitrogen, creatinine, or in white blood cell differential [38].

In an investigator-initiated randomized, placebo-controlled, double-blinded study of 40 healthy men with BMI> 30 kg/m² NR was administered at a dose of 1000mg twice daily for 12 weeks [39]. Adverse events (AEs) were reported in 4 subjects in the NR group which included pruritis, excessive sweating, bloating and transient changes in stool. There were two AEs in the placebo group which were acid reflux and loose stools. The severity was mild in all cases. Laboratory analysis for blood counts and chemistries at 6 weeks revealed no abnormalities in the NR group.

A recent report evaluated a combination of NR with an anti-oxidant pterostilbene (PT; NRPT) in 24 hospitalized patients with AKI with a single dose ranging from 250mg NR, 500mg NR, 750mg NR to 1000mg NR twice a day [15]. Compared to the baseline timepoint, NRPT dose 500 mg/100 mg twice a day increased whole blood NAD+ levels 47% at 48 h, (p = 0.04). Whole blood NAD+ levels in patients with AKI receiving placebo decreased by 50% at 48 h (p = 0.05). Compared to placebo, there was no significant difference in creatinine, estimated glomerular filtration rate (eGFR), electrolytes (sodium, potassium), liver enzymes (ALT, AST, ALP), hemoglobin, white blood count or platelet count in patients treated with NRPT at 48 h. NRPT

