Safety laboratory will be performed at Visit 1 and then every visit thereafter for hospitalized participants. Clinical laboratory tests performed as part of routine clinical care in the 24 hours prior to first study drug dose will be accepted for the baseline (Day 1) safety laboratory tests. Any clinical laboratory tests (see Table 4) performed as part of routine clinical care within the specified visit can be used for safety laboratory testing within the period of hospitalization up to 10 days prior to starting the study drug.

Rationale for specific safety laboratory tests:

Several case studies reported that COVID-19 patients may present with mild symptoms such as muscle weakness with elevated CPK and laboratory confirmation of rhabdomyolysis [75-77]. Although, the incidence of rhabdomyolysis in COVID-19 is not known, several case reports indicate an association between rhabdomyolysis and AKI in COVID-19 patients [78-80]. One study reported elevated levels of CPK in about 14% of patients [21], suggesting involvement of muscle injury.

NR has been evaluated on the development of aging-induced non-alcoholic fatty liver disease in mice [81]. It was found that AST (aspartate transaminase) level was significantly reduced by NR supplementation while the alanine transaminase (ALT) level decreased without significance compared to baseline [81]. One human study demonstrated that NR significantly reduced AST level at day 56 from baseline [8]. It is likely that COVID-19 patients will be receiving different medications for comorbidities and as per the FDA guidance [82], liver function tests will be performed as listed in the Table 4.

Research laboratory tests	Safety laboratory tests	Repository			
Daily during Study Day 1 to Study Day 10					
Blood (daily):	Blood:	Blood:			
1.Whole blood NAD+	1. CPK on day 5	 Future biomarkers 			
2. Serum creatinine	2. Liver function tests on day 5	 Genetic analysis 			
(performed if	3 . Daily CBC and platelets				
routine test is	(performed if routine test is	Urine:			
missed or not	missed or not available)	 Future biomarkers 			
available)					
		Note: additional collections at			
Urine (daily):		hour 3 and hour 6 post-			
1. Urinalysis		randomization study drug for			
2. Urine creatinine		PK analysis			
3. UACR and UPCR					
4. Urine glucose					
5. Lactate					
6. Urine phosphate					
7. Urine NAD+					
metabolome					
Day 30 and Day 90	E				
Blood:		Blood:			
1. Serum creatinine		• Future biomarkers			

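### The plan names only yes/no event tests for safety and specifies no between-arm analysis of platelet count or hemoglobin as measurements, although the complete blood count is taken daily and the possible effect it describes is a small mean fall.

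*Combined protocol and SAP*

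**What the plan says.** Section 9.4.4 (Safety Analyses) consists of a cross-reference: "Please see section 9.4.2 ANALYSIS OF THE PRIMARY EFFICACY ENDPOINT". Under the safety heading of section 9.4.2, the comparison of the probability of a severe graded event "will be tested with Fisher's Exact test, overall and by clinical site". In addition, "treatment groups will be contrasted on the occurrence at least once of each event with Fisher's exact test". Testing is two-sided at 5%. No other between-arm safety test is named.

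Section 2.3.1 reports a dose-escalation study in eight healthy subjects with mean falls in hemoglobin (-0.4 g/dL, p = 0.04), potassium (-0.4 mEq/L, p = 0.015) and "platelet count (-20,000/µL, p = 0.03"). Its list of rare risks, at an unknown rate, includes reductions of under 10% in hemoglobin and platelets.

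The platelet component of the safety endpoint in section 3 is a fall of more than 25% from baseline. The interim analysis in section 9.4.6 uses a count below 50,000/µL instead. Table 4 in section 8.2 lists "Daily CBC and platelets" for Days 1 to 10, and serum electrolytes only at Days 30 and 90.

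Sections 2.1 and 9.2 give a minimally detectable effect size for NAD+. No power figure is given for any safety comparison.

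**The concern.** NAD+, creatinine, eGFR and proteinuria each get a longitudinal analysis in sections 9.4.2 and 9.4.3. Platelet count and hemoglobin are the laboratory values for which section 2.3.1 gives a direction and a size, and they are analysed only through whether an event was recorded. A shift in the mean shows up in such a count only when it pushes someone over a threshold.

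The platelet threshold lies beyond the reported shift. Enrolment requires at least 100,000/µL (section 5.2), so a fall of 20,000/µL is at most 20,000/100,000 = 20% of an eligible baseline. By itself it never reaches 25%; it does so only when added to a participant's own variation.

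All three scenarios in section 2.1 for moving to a Phase IIb or Phase III study include a condition that harm is not significantly increased. When a non-significant test counts as reassurance, an insensitive test favours going ahead.

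**Working it through.** **1. The plan's own figure.** For NAD+ with 40 per arm, (1.960 + 0.842) × √(2/40) = 0.626, against the stated 0.63. The 80% power behind it is not stated, but reproduces it. With 15% withdrawal and 5% attrition (section 5.5), 80/(1 - 0.20) = 100, the number randomized. So 50 per arm is the full sample and 40 per arm the sample after losses.

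**2. Implied variability.** If the p-values in section 2.3.1 come from paired t-tests with n = 8 (an assumption), SD of change = |mean| × √8 / t, with 7 df:
- platelets: 20,000 × 2.828 / 2.715 = 20,800/µL
- hemoglobin: 0.4 × 2.828 / 2.517 = 0.45 g/dL
- potassium: 0.4 × 2.828 / 3.203 = 0.35 mEq/L

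The documents give no SD for hospitalized COVID-19 patients with AKI. I assume two to three times these values.

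**3. Platelets: two analyses of the same daily counts.** Assumptions: normal changes from baseline; a constant shift of -20,000/µL on NR on Days 2–10; within-subject correlation 0.5 to 0.8; baseline 200,000 to 250,000/µL; no missing days.
- Event analysis: a fall above 25% on at least one of the nine days, compared by two-sided Fisher test. This matches the plan's rule of counting an event once.
- Measurement analysis: t-test on each participant's nine-day mean change, whose SD is SD × √(ρ + (1 - ρ)/9).

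For example, at 2× SD and ρ = 0.5 the SD of the mean is 41,700 × 0.745 = 31,100, so d = 20,000/31,100 = 0.64.

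| SD | ρ | Event rate, placebo to NR (baseline 250,000; 200,000) | Fisher / mean, 50 per arm | Fisher / mean, 40 per arm |
|---|---|---|---|---|
| 2× | 0.5 | 29% to 51%; 42% to 65% | 55–58% / 89% | 45–47% / 81% |
| 2× | 0.8 | 18% to 35%; 28% to 48% | 39–44% / 75% | 31–35% / 65% |
| 3× | 0.5 | 52% to 67%; 61% to 75% | 25–27% / 57% | 19–21% / 47% |
| 3× | 0.8 | 36% to 49%; 44% to 58% | 22–23% / 42% | 17–18% / 34% |

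The table enumerates the Fisher test exactly from simulated event rates. Simulating the whole comparison gives about 23–58% for Fisher and 42–90% for the mean at 50 per arm, and 17–49% and 34–81% at 40. The two calculations agree to within two percentage points.

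**4. Sensitivity.** At the implied SD itself (1×), Fisher power at 50 per arm runs from about 11% to 92%, depending on baseline and correlation, while the mean comparison exceeds 99%. The event analysis was weaker in every scenario examined.

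**5. Hemoglobin.** The safety endpoint sets no hemoglobin threshold, so there is no matching event analysis to compute. A simple comparison of a single change of -0.4 g/dL has 60% power (2× SD) or 32% (3×) at 50 per arm, and 51% or 26% at 40.

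**The case against.** A reader might infer that NR is known to lower platelets, hemoglobin and potassium and that the plan would very likely miss it. The documents do not support that.

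- **Evidence for the shifts.** They come from one open-label study of eight healthy subjects, titrated to 1000 mg twice daily; this trial gives 500 mg twice daily. Section 2.3.1 calls the hematologic falls slight and says potassium stayed in the normal range. It also reports no significant difference from placebo in potassium, hemoglobin or platelets at 48 hours in AKI patients. Blood counts and chemistry were similar across groups in the 140-person trial, unchanged in the 21-day study at this trial's dose, and without abnormality on NR in 40 obese men. This stands. The AKI report had only 24 patients and 48 hours, so it does not exclude such shifts over ten days.
- **Likelihood of missing it.** Events are counted at least once over daily measurements, which helps the Fisher test. Its power can exceed 50% within the range above, and the mean comparison can itself fall to 34%. Low power is frequent, not certain.
- **Other coverage.** Section 9.4.1 promises summaries by arm and, in general terms, tabulated treatment effects. CTCAE grading and section 8.3.4 allow clinically significant changes in hemoglobin or potassium to be recorded as adverse events. So it is too strong to say that these values are looked at only as yes/no. But section 9.4.1 names no safety laboratory variable, model or time point, so the comparison is not pre-specified.
- **Potassium.** Table 4 does not schedule it during treatment, and the metabolic panel mentioned in section 8.2 has no timetable. Daily potassium cannot be assumed.

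The plan defines harm as events, and a small shift within the normal range is a different question. That argues for a supporting analysis, not for replacing the endpoint.

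**Conclusion.** The gap is real and moderate in size. The only between-arm safety tests named are Fisher tests on occurrence, and no analysis of platelet count or hemoglobin as a measurement is specified, although both come from a blood count already taken daily. For a platelet fall of 20,000/µL, the event test has about 23–58% power at 50 per arm (17–49% at 40), against about 42–90% (34–81%) for the mean of the daily values.

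The figures rest on paired t-tests behind the reported p-values, SDs two to three times larger in this population, baseline 200,000–250,000/µL, correlation 0.5–0.8 and complete daily counts. Only the 20,000/µL shift and its p-value come from the documents. The ordering of the two analyses did not depend on these choices in any scenario tried; the size of the difference does. The result does not show that NR lowers these values, nor that an effect would very probably be missed.

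**What to change.** Add to sections 9.4.2 and 9.4.4 a supporting safety analysis. For platelet count and hemoglobin, estimate the NR–placebo difference in on-treatment level through Day 10, and at Day 30, with a 95% confidence interval, from a repeated-measures model adjusted for the Day 1 value and site. Report it beside the event counts and in the safety summary for the DSMB. Daily safety laboratory tests apply while participants are hospitalized, so state how values missing after early discharge are handled and report their number by arm.

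Do the same for potassium only where values exist: routine-care results on Days 1–10, and Day 30.

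Present the results as estimates showing which shifts the data exclude, not as new stopping criteria. No dose, threshold or clinical rule changes. The cost is SAP wording and two or three models on data already collected. The downside is a few more comparisons in a plan that, by section 9.4.1, makes no multiplicity correction.
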